1.3 SCHEDULE OF ACTIVITIES (SOA)

In this clinical study, a month is considered to be a period of 4 weeks (28 days).

Table 1 - A - Schedule of activities (up to Year 1)

Procedure	Screening	Baseline/start of IMP	Intervention Phase					Premature End of Treatment ^b	
			M1	M3	M6	M9	M12		
Month (a window of ± 7 days is allowed for all visits after screening)	W-6 to D1^a	D1^a							
Informed consent	X							If switch to Part B	
Visit at clinical site ^c	X	X	X	X	X	X	X	X	X
Inclusion/exclusion criteria	X								
Prior/concomitant medications	X	X	X	X	X	X	X	X	X
Study IMP Administration									
SAR442168 (dispensation and accountability)		X	X	X	X	X	X	If switch to Part B	X (Accountability only)
Safety^c									
Physical examination ^{d, e}	X	X	X	X	X	X	X	X	X
Height	X								
Body weight	X	X	X	X	X	X	X	If needed	X
Vital signs ^e	X	X	X	X	X	X	X	X	X
12-lead ECG ^e	X	X	X	X	X	X	X	If needed	X
Hematology, biochemistry ^{e, f}	X ^g	X ^g	X	X	X	X	X	If needed	X
Urinalysis ^{e, f}	X ^g	X ^g	X	X	X	X	X	If needed	X
β -HCG test (if applicable) ^h	X	X	X	X	X	X	X	If needed	
Serum FSH (if applicable) ⁱ	X								
Suicidality assessment (C-SSRS)	X	X	X	X	X	X	X	If needed	X

Procedure	Screening	Baseline/start of IMP	Intervention Phase					Premature End of Treatment ^b	
			M1	M3	M6	M9	M12		
Month (a window of ± 7 days is allowed for all visits after screening)	W-6 to D1^a	D1^a						UN SCH^b	
Adverse event collection	<----->								
Efficacy									
EDSS		X ^j		X	X	X	X	If MS relapse suspected	X
MRI ^o		X ^j		X	X		X	If needed	X
		X	X	X	X	X	X		
Pharmacokinetics									
SAR442168 pharmacokinetic plasma samples								If MS relapse suspected or in case of index AEs	X ^p
Pharmacodynamics / Biomarkers									
Exploratory biomarkers: [REDACTED]		X ^l						If MS relapse suspected or in case of index AEs	X
Exploratory biomarker plasma samples [REDACTED]		X		X	X		X		X

Abbreviations: AE: adverse event; β -HCG: beta human chorionic gonadotropin; BTK: Bruton's tyrosine kinase; C-SSRS: Columbia Suicide Severity Rating Scale; [REDACTED] D: day; ECG: electrocardiogram; EDSS: Expanded Disability Status Scale; FSH: follicle-stimulating hormone; IMP: investigational medicinal product; M: month; MRI: magnetic resonance imaging; MS: multiple sclerosis; [REDACTED]; [REDACTED] UNSCH: unscheduled; W: week. Note: All assessments shall be done as designated in this SoA unless not permitted according to local regulations.

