- m* For selected sites and participants who consented to the procedure. Refer to [Section 8.1.4](#) for details. This part of the study may be ended prematurely if sufficient data have been gathered.
- n* Once the dose for Part B is known, an unscheduled visit should be performed as quickly as possible (if the next study visit is not due within 4 weeks) to switch participants to part B on the selected dose.
- o* For systemic corticosteroids and adrenocorticotrophic hormone, a 1-month interval is required prior to the MRI scan.
- p* PK to be collected only if pEOT visit can be scheduled within a maximum of 24 hours after the last IMP dose.

Table 2 - B - Schedule of activities (Years 2 to 4)

Procedure	Intervention Phase												UN SCH	Premature End of Treatment ^a
	M15	M18	M21	M24	M27	M30	M33	M36	M39	M42	M45	M48		
Month (a window of ±10 days is allowed)														
Visit at clinical site	X	X	X	X	X	X	X	X		X		X	X	X
Phone call or visit at clinical site									X		X			
Prior/concomitant medications	X	X	X	X	X	X	X	X	X	X	X	X	X	X
Study IMP Administration													X (accountability only)	
SAR442168 (dispensation and accountability)	X	X	X	X	X	X	X	X	X ^j	X	X ^j	X		
Safety														
Physical examination ^{b,c}	X	X	X	X	X	X	X	X		X		X	X	X
Body weight				X				X				X	If needed	X
Vital signs ^c	X	X	X	X	X	X	X	X		X		X	X	X
12-lead ECG ^c	X	X	X	X	X	X	X	X		X		X	If needed	X
Hematology, biochemistry ^c	X	X	X	X	X	X	X	X		X		X	If needed	X
Urinalysis ^c	X	X	X	X	X	X	X	X		X		X	If needed	X
β-HCG test (if applicable) ^d				X				X				X	If needed	
Suicidality assessment (C-SSRS)	X	X	X	X	X	X	X	X		X		X	If needed	X
Adverse event collection	<----->													
Efficacy														
EDSS	X	X	X	X	X	X	X	X		X		X	If MS relapse suspected	X
MRI ^{g, h}		X		X				X				X	If needed	X
████████	X	X	X	X	X	X	X	X		X		X		

Procedure	Intervention Phase												UN SCH	Premature End of Treatment ^a
	M15	M18	M21	M24	M27	M30	M33	M36	M39	M42	M45	M48		
Month (a window of ± 10 days is allowed)														
Pharmacokinetics														
SAR442168 pharmacokinetic plasma samples														If MS relapse suspected or in case of index AEs
Pharmacodynamics / Biomarkers														
Exploratory biomarkers: [REDACTED] [REDACTED] [REDACTED]														If MS relapse suspected or in case of index AEs
Exploratory biomarker plasma samples				X				X			X			X

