Abbreviations: AE: adverse event; β -HCG: beta human chorionic gonadotropin; BTK: Bruton's tyrosine kinase; C-SSRS: Columbia Suicide Severity Rating Scale; [REDACTED] ECG: electrocardiogram; EDSS: Expanded Disability Status Scale; IMP: investigational medicinal product; M: month; MS: multiple sclerosis; MRI: magnetic resonance imaging; [REDACTED]

[REDACTED] UNSCH: unscheduled. Note: All assessments shall be done as designated in this SoA unless not permitted according to local regulations.

a The participant should return for a follow-up visit 4 to 6 weeks after premature end-of-treatment.

b A brief physical examination is sufficient. The brief physical examination should be extended as needed at the judgment of the Investigator in the event of new findings.

c Sample or measurement to be taken before IMP administration.

d Urine β -HCG is sufficient unless a pregnancy is detected or the urine test is inconclusive and a serum test needs to be used for verification or only serum testing is required by local regulation or Institutional Review board (IRB)/International Ethics Committee (IEC).

e Substudy at selected sites.

f For selected sites and participants who consented to the procedure. Refer to [Section 8.1.4](#) for details. This part of the study may be ended prematurely if sufficient data have been gathered.

g For systemic corticosteroids and adrenocorticotropic hormone, a 1-month interval is required prior to the MRI scan.

h Starting from M15 (inclusive), a window of ± 21 days is acceptable for MRI.

i PK to be collected only if pEOT visit can be scheduled within a maximum 24 hours after the last IMP dose.

j Dispensation at site or via direct-to-patient shipment.

Table 3 - C - Schedule of activities (Year 5)

Procedure	Intervention phase						
Month (a window of ± 10 days is allowed)	M51	M54	M57	M60^k	Follow-up visit^k (8 weeks after the last IMP administration)	UNSCH	Premature End of Treatment^a
Visit at clinical site		X		X	X	X	X
Phone call or visit at clinical site	X		X				
Prior/concomitant medications	X	X	X	X	X	X	X
Study IMP Administration							
SAR442168 (dispensation and accountability)	X ^j	X	X ^j	X (accountability only)			
Safety							
Physical examination ^{b, c}		X		X	X	X	X
Body weight				X	X	if needed	X
Vital signs ^c		X		X	X	X	X
12-lead ECG ^c		X		X	X	if needed	X
Hematology, biochemistry ^c		X		X	X	if needed	X
Urinalysis ^c		X		X	X	if needed	X
β -HCG test (if applicable) ^d				X		if needed	

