6.5 CONCOMITANT THERAPY

Any medication or vaccine (including over-the-counter or prescription medicines, vitamins, and/or herbal supplements) that the participant is receiving at the time of enrollment or receives during the study must be recorded along with:

- Reason for use.
- Dates of administration including start and end dates.
- Dosage information including dose and frequency.

Participants must abstain from taking prescription or nonprescription herbal medications containing St. John's wort extract within 14 days before the start of study intervention until completion of the follow-up visit unless, in the opinion of the Investigator and Sponsor, the medication will not interfere with the study.

Therapies for MS noted in the exclusion criterion E03 are not permitted after randomization while the participant is receiving study treatment. Short-term use (3 to 5 days) of glucocorticoids (eg, for MS relapse treatment or an acute illness) and local corticosteroids (eg, cutaneous, nasal, ocular, otic, intra-articular) are allowed.

It is recommended that symptomatic treatments for MS (eg, walking, fatigue, spasticity, incontinence, pain) and/or significant non-drug treatment such as physical therapy, should be maintained at a stable dose or schedule for the duration of the treatment period, if clinically feasible.

Live (attenuated) vaccines should not be administered during the intervention period.

Paracetamol/acetaminophen, at doses of ≤ 3 grams/day and acetylsalicylic acid (aspirin) ≤ 81 mg/day are permitted for use at any time during the study. A short courses (up to 5 days) of NSAIDs (other than acetylsalicylic acid > 81 mg/day), preferably selective cyclooxygenase-2 inhibitors at the lowest effective dose, may be given during the course of the study if clinically

necessary for the treatment of an existing medical condition or a new event. The Investigator must record the use of NSAIDs (and any other comedication) in the eCRF. Other concomitant medication may be considered on a case-by-case basis by the Investigator in consultation with the medical monitor if required.

In addition, [Section 5.2](#) contains a list of prohibited anticoagulant/antiplatelet therapies in this study.

CYP inhibitor/inducer

Potent and moderate inducers of CYP3A or potent inhibitors of CYP2C8 hepatic enzymes are not allowed throughout the study ([Appendix 7, Section 10.7](#)).

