2.4.4 Analysis of efficacy endpoints

The primary objective of this LTS16004 study is to evaluate safety. Efficacy data will be summarized with appropriate measures of variability.

For by visit summaries including data from DRI15928, visits during the DRI15928 period correspond to weeks on tolebrutinib treatment.

MRI variables

Number and volume of lesions will be summarized by visit using descriptive statistics in the mITT population including data from both DRI15928 and LTS16004. For parameters with a baseline value, change and/or percent change from baseline will be included. For new/enlarging T2 lesions, the values will be standardized to per month values by dividing by the number of months (4-week intervals) from the previous MRI to the current MRI. In addition, average number of lesions per scan (new Gd-enhancing T1 hyperintense and new T1 non-enhancing hypointense) or annualized rate of lesions (new/enlarging T2) will be summarized descriptively. Graphical presentations may be used to illustrate trends over time.

Values for Gd-enhancing T1 lesions will be excluded if the participant had a suspected MS relapse and was receiving systemic corticosteroids within the 30 days prior to the MRI assessment date given the short-term effects of systemic corticosteroids on Gd-enhancing lesions.

Listings of MTR recovery and number of phase rim lesions will be provided.

For each dose group and overall, the percentage of participants with no new MRI disease activity will be provided by visit.

Time course of intensity related parameters and MTR recovery will be modeled using generalized linear mixed modeling. Annualized brain volume loss will be modeled as well.

Annualized MS relapse rate

A gross estimate of ARR is the total number of relapses for participants by dose group divided by the sum of the standardized study duration for participants in the dose group.

Total number of confirmed relapses and standardized study duration will be calculated for each participant as:

- Total number of confirmed relapses is defined as number of confirmed relapses with onset between first IMP date and treatment discontinuation/completion date (same as last dose intake date) in LTS16004.
- Standardized study duration (in years) will be calculated by $(\text{last dose intake date} - \text{first IMP date} + 1) / 365.25$ in LTS16004.

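### Gd-enhancing values are excluded only when steroids coincide with a suspected relapse, although the SAP's reason covers steroids given for any indication (minor)

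*SAP*

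**What the plan says.** SAP 2.4.4, under MRI variables, gives one exclusion rule for enhancing lesions: "Values for Gd-enhancing T1 lesions will be excluded if the participant had a suspected MS relapse and was receiving systemic corticosteroids". The look-back period and the reason come later in that sentence: "within the 30 days prior to the MRI assessment date given the short-term effects of systemic corticosteroids on Gd-enhancing lesions". Relapse and steroid use are joined by an and, while the reason names the steroid alone.

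Protocol 6.5 permits glucocorticoid courses of 3 to 5 days and gives as examples "for MS relapse treatment or an acute illness". So steroids without a relapse are an expected event in this study.

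The protocol also has a scheduling rule that does not depend on the indication. Table 1 footnote o of Section 1.3 reads: "For systemic corticosteroids and adrenocorticotrophic hormone, a 1-month interval is required prior to the MRI scan". Footnote g of Tables 2 and 3 repeats it for Years 2 to 5. Section 1.3 defines a month as 28 days.

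The endpoints that use these values (SAP 2.1.3.1) are the number of new Gd-enhancing lesions and the total number of Gd-enhancing lesions, both secondary. The proportion of participants without new MRI activity, which is exploratory, also requires a new-Gd count of zero.

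**The concern.** If steroids in the preceding 30 days make a Gd count unreliable, they do so whether they were given for a relapse or for another illness. As written, the rule discards the first kind of scan and keeps the second. A retained scan enters the by-visit summaries and the average lesions per scan, and it can count as a visit without new MRI activity.

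Protocol 2.1 states an aim of showing that the MRI benefit is maintained, and there is no concurrent untreated arm. If steroids lower enhancement, as the exclusion implies, the retained scans would lean towards that conclusion.

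**Working it through.** The plan states no figure on this point that could be reproduced. The check is a comparison of texts, followed by a rough count for scale.

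**Texts side by side**

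| Source | Drugs covered | Indication | Interval before MRI |
|---|---|---|---|
| Protocol 1.3, footnotes o and g | Systemic corticosteroids, ACTH | Any | 1 month (28 days) |
| SAP 2.4.4, stated reason | Systemic corticosteroids | Any | Short term |
| SAP 2.4.4, rule | Systemic corticosteroids | Suspected relapse only | 30 days |

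The rule is narrower than both its own reason and the protocol. No other SAP section fills the gap. Section 2.2.1 counts and lists critical or major deviations but removes no values. Section 2.5.4 takes unscheduled laboratory, vital-sign and ECG data out of the by-visit summaries but does not mention MRI.

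**How such scans can arise despite the 1-month interval**

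1. In Year 1, "a window of ± 7 days is allowed for all visits after screening". Suppose a course ends x days before the target date of the M3, M6 or M12 scan. The latest in-window scan is x + 7 days after the course, which reaches 28 only if x is at least 21. The earliest in-window scan is 7 days before target, so a course ending at x = 8 or more precedes every in-window scan. For x from 8 to 20, either the window or the interval is breached.
2. A scan 29 or 30 days after a course meets the 28-day interval but still lies inside the SAP's 30-day look-back.
3. MRI is also listed for unscheduled visits, if needed, and for premature end of treatment.

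**Scale**

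Inputs from the documents: 126 enrolled (SAP 1.3), and 8 scheduled scans after Day 1, at M3, M6, M12, M18, M24, M36, M48 and M60 (protocol Tables 1 to 3). The maximum is 126 × 8 = 1,008 scans. The rate r of non-relapse steroid courses per participant-year is not in the documents and is assumed.

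Chance that a scan falls within 30 days after a course: p = 1 − exp(−r × 30/365.25). Affected scans = 1,008 × p. Affected scans per visit = 126 × p.

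| Assumed r | p | Scans of 1,008 | Per visit of 126 |
|---|---|---|---|
| 0.02 | 0.0016 | 1.7 | 0.21 |
| 0.05 | 0.0041 | 4.1 | 0.52 |
| 0.10 | 0.0082 | 8.2 | 1.03 |
| 0.20 | 0.0163 | 16.4 | 2.05 |

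The linear form 1,008 × r × 30/365.25 gives 4.1, 8.3 and 16.6 for the last three rows, hence about 4 to 17. Both forms assume no dropout and course timing unrelated to scan timing, that is, no adherence to the interval. They treat a course as one day. Counting all 5 days of the longest permitted course scales the counts by 35/30, to about 5 to 19, which does not change the conclusion. Unscheduled and end-of-treatment scans are not counted.

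If affected scans would otherwise have the average count, the mean Gd count is understated by the fraction p × s, where s is the share of enhancement suppressed. For r from 0.05 to 0.20 this is 0.41% to 1.63% with s = 1, and 0.20% to 0.81% with s = 0.5.

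**The case against.** The best reply is that the protocol already controls the exposure. The 1-month interval applies to every indication, and from M15 the MRI window widens to ±21 days, which leaves more room to move a scan. A scan soon after non-relapse steroids therefore gets in mainly by breach. The affected endpoints are secondary or exploratory in a safety extension, SAP 2.4 calculates no p-values, and SAP 3 calls the study supportive.

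All of that stands, and it limits the size. It does not remove the gap. The interval applies equally to steroids given for relapse, and the SAP still wrote an exclusion rule for those scans. The SAP thus expects such scans and handles only one kind.

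Three stronger readings are tempting, and the documents do not support them:

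- A reader might infer that the rule also biases results by removing the most active scans, those around relapses. It removes only relapse scans with recent steroids; relapse scans without steroids stay in. Widening the rule would remove the same scans, so their removal is not a fault of the relapse condition. Nothing in the documents shows that they are the most active.
- A reader might infer that both secondary Gd endpoints are biased as a matter of fact. That needs affected scans, whose number is unknown. The SAP speaks of short-term effects without giving a direction; that the effect lowers counts is implied only.
- A reader might see the omission of ACTH as a second defect of substance. Exclusion criterion E03 lists ACTH, and protocol 6.5 bars the MS therapies noted in E03 during treatment, so its use would ordinarily be a deviation. Adding it is for consistency.

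**Conclusion.** The point holds as a minor mismatch. The SAP's exclusion of Gd-enhancing values is narrower than the reason it gives, and scans soon after steroids for another illness are kept in two secondary counts and one exploratory proportion.

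The likely effect is very small: about 4 to 17 of at most 1,008 scheduled scans, or 0.4% to 1.6%, roughly 0.5 to 2 per visit if all 126 participants are scanned. This rests on an assumed 0.05 to 0.20 non-relapse courses per participant-year, no dropout and no adherence to the 1-month interval. Adherence would reduce it further. The reason to act is that the handling of these scans should be settled before database lock, not scan by scan afterwards.

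**What to change.** In SAP 2.4.4, delete the suspected-relapse condition. Exclude Gd-enhancing values from any scan with systemic corticosteroid use in the 30 days before the MRI, whatever the indication, and name ACTH alongside corticosteroids to match the protocol footnotes.

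Keep the window at 30 days. Rewording it as 1 month would shorten it to 28 days under the protocol's definition.

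Apply the same rule to the proportion without new MRI activity, and say how a visit with an excluded Gd value is classified. Report the number of scans excluded.

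The cost is SAP wording and programming against medication dates and reasons for use, which protocol 6.5 already requires sites to record. A few more scans drop out of the Gd summaries. No study procedure or treatment rule changes.

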3 OBJECTIVES AND ENDPOINTS

Table 6 - Objectives and endpoints

Objectives	Endpoints
Primary	

To determine the long-term safety and tolerability of SAR442168 in RMS participants	Adverse events (AEs), serious adverse events (SAEs), safety findings on magnetic resonance imaging (MRI), potentially clinically significant abnormalities (PCSA) in laboratory tests, electrocardiogram (ECG), or vital signs during the study period.
Secondary	
To evaluate efficacy of SAR442168 on disease activity, assessed by clinical and imaging methods.Number of new gadolinium (Gd)-enhancing T1-hyperintense lesions by brain MRI.Number of new or enlarging T2 lesions.Total number of Gd-enhancing T1-hyperintense lesions.Number of relapses (annualized relapse rate [ARR]) during the study period.Change in Expanded Disability Status Scale (EDSS) score from baseline over time.
Tertiary/exploratory To evaluate efficacy of SAR442168 on disease activity and the pharmacodynamics (PD) of SAR442168.	
[REDACTED] in case of index AEs (cytopenia and arrhythmias).[REDACTED][REDACTED]Change in volume of T2-lesions from baseline over time.Change in brain volume, including regional changes, over time.Change in the number of T1-hypointense lesions from Baseline over time.Change in myelin integrity and other features of MRI lesions as measured by magnetization transfer ratio and susceptibility-weighted imaging MRI over time.Proportion of participants with no new MRI disease activity through the end of the study.Proportion of relapse-free participants through the end of the study.[REDACTED][REDACTED]

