7.1 DISCONTINUATION OF STUDY INTERVENTION

7.1.1 Definitive discontinuation

The IMP should be continued whenever possible.

In case the IMP is stopped, it should be determined whether the stop can be made temporarily; definitive IMP discontinuation should be a last resort. Any IMP discontinuation must be fully documented in the eCRF. In any case, the participant should remain in the study as long as possible.

Definitive intervention discontinuation is any intervention discontinuation associated with the definitive decision from the Investigator not to re-expose the participant to the IMP at any time during the study, or from the participant not to be re-exposed to the IMP, whatever the reason.

Discontinuation of study intervention for abnormal liver function should be considered by the Investigator when a participant meets one of the conditions outlined in [Section 10.6](#) or if the Investigator believes that it is in best interest of the participant.

If a clinically significant finding is identified in the ECG (including, but not limited to changes from baseline in QT interval corrected using Fridericia's formula [QTcF]) after enrollment, the Investigator or qualified designee will determine if the participant can continue in the study and if any change in participant management is needed. Review of ECG findings by a cardiologist needs to be taken into consideration for a decision of a definitive discontinuation of study intervention because of ECG changes. This review of the ECG printed at the time of collection must be documented. Any new clinically relevant finding should be reported as an AE.

See the schedule of activities (SoA) ([Section 1.3](#)) for data to be collected at the time of intervention discontinuation and follow-up and for any further evaluations that need to be completed.

Any abnormal laboratory value or ECG parameter will be confirmed within 24 hours to inform the decision whether to discontinue the IMP for the concerned participant.

In case of premature discontinuation of the intervention, the end-of-treatment visit will be conducted.

Handling of participants after definitive intervention discontinuation

Participants will be followed-up according to the study procedures specified in this protocol up to the scheduled date of study completion, or up to recovery or stabilization of any AE to be followed-up as specified in this protocol, whichever comes last.

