2.1.4 Safety endpoints

The safety analyses will be based on the reported AEs, including safety findings on MRI, and other safety information, such as clinical laboratory, ECG, vital signs, and C-SSRS data collected in LTS16004.

Magnetic resonance imaging scans should be reviewed locally for any non-MS pathology. In case of such findings, the relevant information needs to be provided to the Investigator for appropriate safety reporting and to ensure the appropriate management of the participant's identified safety finding. When available, a diagnosis of pathology as a cause of such MRI findings or the findings themselves will be reported as an AE until the diagnosis is clear.

MS relapses are exempt from being reported as AE/SAE unless, in the judgment of the Investigator, it is unusually severe or medically unexpected. MS relapses are collected on the eCRF and analyzed as part of the efficacy analyses.

Observation periods

In general, there should be no pretreatment AEs in the LTS16004 study since participants were to roll directly into LTS16004 after completing the DRI15928 study. However, in case there is a gap, the pre-treatment period for the LTS16004 study is defined as the time from signing the ICF until first IMP intake in the LTS16004 study.

The on-treatment period is from first administration of tolebrutinib in the LTS16004 study to the last administration +10 days, including both Part A and Part B treatment periods.

The post-treatment period, if applicable, is from the end of the on-treatment period to the end of the follow-up in LTS16004.

The on-study period is from signing the ICF to the end of follow-up in the LTS16004 study.

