ARR will be analyzed using a negative binomial regression model in the mITT population. The model will include the total number of confirmed relapses with onset between first and last IMP doses in LTS16004 as response variable and dose group (5/60, 15/60, 30/60, and 60/60 mg) as covariate. Log transformed standardized treatment duration will be included in the model as an "offset" variable. The estimated ARR for each dose group and corresponding 95% 2-sided CI will be derived from the negative binomial model. The relative reductions in ARR (60/60 mg versus each other dose group) along with 95% CIs will be estimated from the model.

Number of participants with 0, 1, 2, 3, 4, or ≥ 5 relapses will be presented by dose group, namely, 5/60, 15/60, 30/60, and 60/60 mg.

The ARR for the tolebrutinib 60 mg treatment period will be analyzed using a negative binomial regression model, as well. Only relapses with onset during the tolebrutinib 60 mg treatment period will be counted, which means Part B only for participants originally assigned to 5, 15 and 30 mg dose groups and Parts A and B for participants originally assigned to the 60 mg dose group. Excluded are patient years and relapses during the first 8 weeks of tolebrutinib treatment after the switch to Part B for participants in the 5/15/30 to 60 mg groups and the same for participants in the 60/60 mg dose group, if the sum of the placebo run-out period (if applicable) and any gap period is >4 weeks. The negative binomial regression model will use total number of relapses as the response variable and log transformed standardized treatment duration as an "offset" variable. The estimated ARR and the 95% CI will be provided.

The number of participants with 0, 1, 2, 3, 4, or ≥ 5 relapses during the tolebrutinib 60 mg treatment period will also be presented.

Proportion of participants relapse free

Time to first confirmed relapse in LTS16004 is defined as "the date of first relapse - first IMP date (in LTS16004) + 1". If the participant has no relapse before treatment discontinuation/completion, then the participant will be considered as free of relapse until the date of treatment discontinuation/completion. His/her data will be censored after this date. The proportion of participants without confirmed relapse in LTS16004 will be estimated based on the Kaplan-Meier curve at yearly time points (1, 2, 3, 4 and 5 years since first IMP in LTS16004).

Change from baseline in EDSS scores

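### Relapses starting after the last dose are left out of ARR and relapse-free, although the protocol sets both over the whole study; ordinary ones have no output that clearly reports them

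*SAP*

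**What the plan says.** **Protocol.** Table 6 (section 3) lists the secondary endpoint as "Number of relapses (annualized relapse rate [ARR]) during the study period", and the exploratory relapse-free endpoint runs to the end of the study. On stopping drug, section 7.1.1 states: "Participants will be followed-up according to the study procedures specified in this protocol up to the scheduled date of study completion". Sections 7.1.2.1 and 7.2 likewise keep or encourage such participants in the study. Section 8.1.2.1 sends every relapse to a dedicated eCRF page. Sections 8.2 and 8.3.9 keep relapses out of AE reporting unless they are SAEs, because they are analysed as efficacy.

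**SAP.** Section 2.1.3.2 defines ARR and relapse-free within LTS16004 and names no cut-off at last dose. Section 2.4.4 then adds one:

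- For the gross ARR: "Total number of confirmed relapses is defined as number of confirmed relapses with onset between first IMP date and treatment discontinuation/completion date". The SAP equates that end date with the date of the last dose.
- The negative binomial model takes the "total number of confirmed relapses with onset between first and last IMP doses in LTS16004 as response variable", with treatment duration as offset.
- The supplementary 60 mg ARR counts relapses only during 60 mg treatment.
- For a participant with no relapse on treatment, the Kaplan-Meier rule is that "the participant will be considered as free of relapse until the date of treatment discontinuation/completion. His/her data will be censored after this date".

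On the safety side, section 2.1.4 says: "MS relapses are exempt from being reported as AE/SAE unless, in the judgment of the Investigator, it is unusually severe or medically unexpected". Section 2.5.1 sets a different window for participants in Ukraine and Russia lost to follow-up because of the emergency: their relapses and time count to last contact.

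**The concern.** Two rules, each reasonable alone, leave a gap together. Ordinary relapses are excused from AE reporting because the efficacy analysis will cover them. For relapses after the last dose, SAP 2.4.4 then takes that efficacy analysis away. The events are collected, but the plan gives them no clear place in the report.

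The SAP also answers a narrower question than the protocol asks. The protocol's endpoints cover the study; the SAP's cover time on drug. Neither SAP 1.5 nor 1.6 mentions this. In a long-term study whose primary objective is safety, disease activity after stopping is something readers will look for, and the planned outputs could not tell them whether it was low, high or unobserved.

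**Working it through.** The documents give no relapse rate, expected event count or discontinuation rate, so there is no planned figure to reproduce. The check has two parts.

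**1. Where can a relapse after the last dose appear?**

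- *ARR (gross and model) and 60 mg ARR, SAP 2.4.4:* excluded by the onset window.
- *Relapse-free curve, SAP 2.4.4:* excluded by censoring.
- *Relapse-count table by dose group, SAP 2.4.4, and steroid-treated relapse table, SAP 2.4.2:* no onset window is stated, so inclusion is unclear.
- *Ukraine/Russia participants lost to follow-up, SAP 2.5.1:* included in ARR and relapse-free up to last contact.
- *AE outputs, SAP 2.1.4 and 2.4.5.1:* included only if the relapse is reportable as an AE or SAE. Up to 10 days after last dose it is then a TEAE; later it is in the post-treatment summary and listing. If serious, it is also in the listing of all SAEs. Protocol 8.3.9 narrows this route, since hospitalization done routinely for relapse does not make it serious.

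A non-serious relapse after the last dose that is neither unusually severe nor unexpected thus has no output that clearly includes it. By contrast, SAP 2.4.4 states no last-dose cut-off for MRI or EDSS.

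**2. How many relapses might this be?**

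From the documents: 126 enrolled (SAP 1.3); Month 60 is day 1680 (SAP Table 2), so 1680/365.25 = 4.60 years. Everything else here is assumed.

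Formula: relapses left out = stoppers × off-drug years × off-drug rate. Assume 15 to 35 stoppers and 0.15 to 0.30 relapses per year.

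- *Follow-up ends at 6 weeks* (the upper end of the 4-to-6-week visit after premature end of treatment in the schedule of activities):
  - low: 15 × 42/365.25 × 0.15 = 0.26
  - high: 35 × 42/365.25 × 0.30 = 1.2
- *Follow-up lasts 1 to 2.5 years* (assumed for follow-up to scheduled completion under Protocol 7.1.1):
  - low: 15 × 1.0 × 0.15 = 2.3
  - high: 35 × 2.5 × 0.30 = 26.3

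For scale, assuming 85% mean retention and an on-drug ARR of 0.10 to 0.20, on-drug relapses = 126 × 0.85 × 4.60 × 0.10 = 49, or 99 at 0.20.

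**Effect on the rate itself.** A second illustration assumes 10%, 20% or 30% stop at mid-study (day 840), with an on-drug ARR of 0.20.

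- Off-drug person-years if followed to day 1680: 126 × 0.10 × 840/365.25 = 29.0; likewise 58.0 and 86.9.
- Matching on-drug person-years: 550.6, 521.6 and 492.6.
- Study-period ARR = (on-drug years × 0.20 + off-drug years × off-drug rate) / total years:
  - off-drug rate 0.20: ARR stays at 0.20
  - off-drug rate 0.5: 0.215, 0.23 and 0.245
  - off-drug rate 1.0: 0.24, 0.28 and 0.32
- If follow-up stops at 6 weeks, off-drug time is only 1.45 to 4.35 person-years. The largest case gives (492.6 × 0.20 + 4.35 × 1.0)/(492.6 + 4.35) = 0.207.

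**The case against.** The on-treatment window is a legitimate choice. The secondary objective is the efficacy of the drug, numerator and denominator cover the same time, Protocol 8.1.2.2 leaves the details of relapse analysis to the SAP, and the SAP's rule of using data up to closeout (2.1.3) yields where the SAP specifies otherwise. Relapses off drug may occur on another MS therapy, because Protocol 6.5 bars those therapies only while study treatment continues; such relapses would not measure the effect of stopping. The study is descriptive, without hypotheses or p-values. All of this stands, and it is why the on-treatment ARR should be kept.

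Three stronger readings are tempting but not supported:

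- *That relapses after the last dose appear in no table at all.* Serious, unusually severe or unexpected ones reach the AE/SAE outputs, section 2.5.1 counts one subgroup to last contact, and two tables state no window.
- *That the plan hides rebound after stopping.* The documents do not describe rebound as an effect of this drug, and a report without such a table is silent; it does not claim an absence of events.
- *That many relapses must be lost.* The schedule of activities shows one follow-up visit 4 to 6 weeks after premature end of treatment, and completers who join the Phase 3 extension have no follow-up visit (Table 3, footnote k). Off-drug time could be very short.

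The objection does not answer the mismatch with Table 6, or the absence of a clear output for ordinary relapses that the protocol requires sites to record.

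**Conclusion.** The point holds as a gap between protocol endpoint and SAP analysis, and as a reporting gap. It is not a calculation error and does not bias the on-treatment estimate. The protocol's study-period ARR and end-of-study relapse-free proportion are replaced by on-treatment versions without explanation.

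The consequence ranges from negligible (under about 1 relapse) to material (some 26 relapses beside 49 to 99 on drug), depending mainly on how long participants who stop are actually followed. Those figures rest on assumed numbers of stoppers, follow-up times, retention and relapse rates. If the off-drug rate equals the on-drug rate, the ARR does not move. The case for acting is that the fix is cheap and lets the report show which situation applies.

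**What to change.** In SAP 2.4.4:

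1. Keep the current ARR and relapse-free analyses and label them as on-treatment.
2. Add supplementary study-period versions, from first LTS16004 dose to end of follow-up, to match protocol Table 6.
3. Add one table and one listing of confirmed relapses with onset after last dose: number, off-drug person-time, days since last dose, and whether another MS therapy had started. Present these descriptively.
4. State the onset window for the relapse-count table, and in SAP 2.4.2 for the steroid-treated relapse table.
5. Record in SAP 1.6 that the main analyses use a narrower window than the protocol endpoints, and why.

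The cost is SAP wording and a little programming. The relapses are already on their own eCRF page. Person-time needs dose and last-contact dates, and the therapy column needs MS treatment recorded after the last dose. No existing estimate changes.
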